10.1 Regulatory and ethical compliance

This clinical study was designed and shall be implemented, executed and reported in accordance with the ICH Harmonized Tripartite Guidelines for Good Clinical Practice, with applicable local regulations (including European Directive 2001/20/EC, US CFR 21, and Japanese Ministry of Health, Labor, and Welfare), and with the ethical principles laid down in the Declaration of Helsinki.

10.2 Informed consent procedures

Eligible patients/subjects may only be included in the study after providing written (witnessed, where required by law or regulation), IRB/IEC-approved informed consent, or, if applicable after such consent has been provided by a legally acceptable representative(s) of the patient. In cases where the patient's representative gives consent, the patient must be informed about the study to the extent possible given his/her understanding. If the patient is capable of doing so, he/she must indicate assent by personally signing and dating the written informed consent document or a separate assent form. Informed consent must be obtained before conducting any study-specific procedures (e.g., all of the procedures described in the protocol). The process of obtaining informed consent must be documented in the patient source documents.

Novartis will provide to investigators in a separate document a proposed ICF23 that complies with the ICH GCP guideline and regulatory requirements and is considered appropriate for this study. Any changes to the proposed consent form suggested by the investigator must be agreed to by Novartis before submission to the IRB/IEC, and a copy of the approved version must be provided to the Novartis monitor after IRB/IEC approval.

Women of child bearing potential must be informed that taking the fingolimod treatment may involve unknown risks to the fetus if pregnancy were to occur during the study and agree that in order to participate in the study they must adhere to the contraception requirement for the duration of the study. If there is any question that the patient will not reliably comply, they must not be entered in the study.

10.3 Responsibilities of the investigator and IRB/IEC

Before initiating a trial, the investigator/institution must obtain approval/favorable opinion from the Institutional Review Board/Independent Ethics Committee (IRB/IEC) for the trial protocol, written informed consent form, consent form updates, subject recruitment procedures (e.g., advertisements) and any other written information to be provided to patients/subjects. Prior to study start, the investigator is required to sign a protocol signature page confirming his/her agreement to conduct the study in accordance with these documents and all of the instructions and procedures found in this protocol and to give access to all relevant data and records to Novartis monitors, auditors, Novartis Quality Assurance representatives, designated agents of Novartis, IRBs/IECs, and regulatory authorities as required. If an inspection of the clinical site

is requested by a regulatory authority, the investigator must inform Novartis immediately that this request has been made.

10.4 Publication of study protocol and results

The key design elements of this protocol will be posted in a publicly accessible database such as clinicaltrials.gov. In addition, upon study completion and finalization of the study report the results of this trial will be either submitted for publication and/or posted in a publicly accessible database of clinical trial results.

10.5 Quality Control and Quality Assurance

Novartis maintains a robust Quality Management (QM) system that includes all activities involved in quality assurance and quality control, including the assignment of roles and responsibilities, the reporting of results, and the documentation of actions and escalation of issues identified during the review of quality metrics, incidents, audits and inspections.

Audits of investigator sites, vendors, and Novartis systems are performed by Novartis Pharma Auditing and Compliance Quality Assurance, a group independent from those involved in conducting, monitoring or performing quality control of the clinical trial. The clinical audit process uses a knowledge/risk based approach.

Audits are conducted to assess GCP compliance with global and local regulatory requirements, protocols and internal SOPs, and are performed according to written Novartis processes.

11 Protocol adherence

This protocol defines the study objectives, the study procedures and the data to be collected on study participants. Additional assessments required to ensure safety of patients/subjects should be administered as deemed necessary on a case by case basis. Under no circumstances is an investigator allowed to collect additional data or conduct any additional procedures for any research related purpose involving any investigational drugs under the protocol.

Investigators ascertain they will apply due diligence to avoid protocol deviations. If an investigator feels a protocol deviation would improve the conduct of the study this must be considered a protocol amendment, and unless such an amendment is agreed upon by Novartis and approved by the IRB/IEC and health authorities, where required, it cannot be implemented.

≥ 2 attacks, objective clinical evidence of ≥ 2 lesions or objective clinical evidence of 1 lesion with reasonable historical evidence of a prior attack	None
≥ 2 attacks; objective clinical evidence of 1 lesion	Dissemination in space (DIS) demonstrated by: ≥ 1 T2 lesion in at least 2 of 4 MS typical regions of the CNS (periventricular, juxtacortical, infratentorial, spinal cord); OR Await a further clinical attack implicating a different CNS site
1 attack, objective clinical evidence of ≥ 2 lesions	Dissemination in time (DIT) demonstrated by: Simultaneous presence of asymptomatic gadolinium-enhancing and non-enhancing lesions at any time; OR A new T2 and / or gadolinium-enhancing lesion(s) on follow up MRI, irrespective of its timing with reference to a baseline scan; OR Await a second clinical attack
1 attack, objective clinical evidence of 1 lesion (clinically isolated syndrome)	Dissemination in space and time demonstrated by: For DIS: ≥ 1 T2 lesion in at least 2 of 4MS typical CNS regions (periventricular, juxtacortical, infratentorial, spinal cord); OR Await a second clinical attack implicating a different CNS site AND For DIT: Simultaneous presence of asymptomatic gadolinium-enhancing and non-enhancing lesions at any time; OR A new T2 and / or gadolinium-enhancing lesion(s) on follow up MRI, irrespective of its timing with reference to a baseline scan; OR Await a second clinical attack
Insidious neurological progression suggestive of MS (PPMS)	One year of disease progression (retrospectively or prospectively) AND 2 out of 3 of the following criteria: 1. Evidence of DIS in the brain based on ≥ 1 T2 lesion in MS-characteristic regions (periventricular, juxtacortical or infratentorial); 2. Evidence of DIS in the spinal cord based on ≥ 2 T2 lesions in the cord; 3. Positive CSF (isoelectric focusing evidence of oligoclonal bands and/or elevated IgG index)

14 Appendix 2: Clinically notable laboratory values

Only selected lab parameters identified as notable which have been shown to be sensitive to fingolimod exposure are included.

Laboratory Variable	Standard Units	SI Units
Hematology variables		
Hemoglobin	≤10.0 g/dL	≤100 g/L
Platelets	≤100 k/mm ³	≤100 x 10 ⁹ /L
	≥600 k/mm ³	≥600 x 10 ⁹ /L
White Blood Cells	≤2.0 k/mm ³	≤2.0 x 10 ⁹ /L
	≥15 k/mm ³	≥15 x 10 ⁹ /L

Hematology variables - differential

Neutrophils	≤ 1,000 /mm ³	≤1 x 10 ⁹ /L
	≥12000/mm ³	≥12 x 10 ⁹ /L
Lymphocytes	<200/mm ³	<0.2 x 10 ⁹ /L
	≥8000/mm ³	≥8 x 10 ⁹ /L

15 Appendix 3: Patient Determined Disease Steps (PDDS)

Please read the choices listed below and choose the one that best describes your own situation. This scale focuses mainly on how well you walk. You might not find a description that reflects your condition exactly, but please mark the one category that describes your situation the closest.

0	Normal	I may have some mild symptoms, mostly sensory due to MS but they do not limit my activity. If I do have an attack, I return to normal when the attack has passed.
1	Mild Disability	I have some noticeable symptoms from my MS but they are minor and have only a small effect on my lifestyle.
2	Moderate Disability	I don't have any limitations in my walking ability. However, I do have significant problems due to MS that limit daily activities in other ways.
3	Gait Disability	MS does interfere with my activities, especially my walking. I can work a full day, but athletic or physically demanding activities are more difficult than they used to be. I usually don't need a cane or other assistance to walk, but I might need some assistance during an attack
4	Early Cane	I use a cane or a single crutch or some other form of support (such as touching a wall or leaning on someone's arm) for walking all the time or part of the time, especially when walking outside. I think I can walk 25 feet in 20 seconds without a cane or crutch. I always need some assistance (cane or crutch) if I want to walk as far as 3 blocks
5	Late Cane	To be able to walk 25 feet, I have to have a cane, crutch or someone to hold onto. I can get around the house or other buildings by holding onto furniture or touching the walls for support. I may use a scooter or wheelchair if I want to go greater distances.
6	Bilateral Support	To be able to walk as far as 25 feet I must have 2 canes or crutches or a walker. I may use a scooter or wheelchair for longer distances.
7	Wheelchair/Scooter	My main form of mobility is a wheelchair. I may be able to stand and/or take one or two steps, but I can't walk 25 feet, even with crutches or a walker.
8	Bedridden	Unable to sit in a wheelchair for more than one hour.

ANCOVA	analysis of covariance
CSR	Clinical Study report
FAS	Full Analysis Set
eCRF	Electronic Case Report Form
MedDRA	Medical Dictionary for Drug Regulatory Affairs
NCI	National Cancer Institute
o.d.	Once Daily
qd	Qua'que di'e / once a day
SAP	Statistical Analysis Plan
SOC	System Organ Class
TFLs	Tables, Figures, Listings
WHO	World Health Organization

1 Introduction

This Statistical Analysis Plan (SAP) outlines the planned methods and reports to be used in the statistical analysis of study “CFTY720US40”. The purpose of the SAP is to document in details the statistical methods and analysis conventions to be used in the completion of the Clinical Study Report (CSR). Specifically, this document will:

1. Briefly review the objectives, design and endpoints of the study
2. Describe the targeted overall patient enrollment
3. Define the analysis populations
4. Define the rules for determining the outcome of the endpoints
5. Provide an overview of the planned primary, secondary and exploratory statistical analyses.

The reader of this SAP is encouraged to also read the clinical protocol for details on conduct of this study.

1.1 Study design

This study uses a two-cohort, nonrandomized, open-label multicenter design. Patients will be enrolled from up to 125 sites in the United States. The study consists of two periods: screening (up to 4 Weeks) and fingolimod treatment period (Baseline to 12 Months). The total study duration is up to 13 Months. Follow-up Visits will be conducted at 3, 6 and 12 Months. Fingolimod treatment includes two cohorts. In the first cohort approximately 200 patients with RMS, who are newly prescribed commercially available fingolimod 0.5mg/day will participate in the study. In the second cohort approximately 200 RMS patients who have been on commercially available fingolimod 0.5mg/day continuously for at least ≥ 2 years will participate in the study. Cohort 2 will only serve as a referent cohort for Cohort 1 and is not intended to be a direct Cohort 1 comparator as no a priori hypotheses are to be examined.

1.2 Study objectives and endpoints

The primary objective of this study aims to characterize phenotypic changes in the cellular components (biomarkers) of the innate (monocytes, neutrophils and NK cells) and adaptive (peripheral blood T cells, B cells) immune system including their subtypes, in patients with RMS, initiating fingolimod therapy of 0.5mg/day up to 12 Months of treatment (Cohort 1) and those patients who have been on fingolimod 0.5mg/day continuously for ≥ 2 years (Cohort 2). Both cohorts will continue treatment for the next 12 Months.

Secondary objectives are to investigate the association between anti-John Cunningham virus (JCV) antibody status/index and phenotypic changes in innate and T and B cell subsets in patients on fingolimod therapy.

2 Statistical methods

2.1 Data analysis general information

Interim analysis/final analysis will be performed [REDACTED]

SAS® Software version 9.4 or later will be used in this study as primary statistical analysis software.

Statistical methods used in reporting for both efficacy and safety are described below.

In general, categorical measurements will be summarized by frequency counts and percentages. Continuous variables will be summarized by numbers of patients, means, standard deviations, standard error of mean, first quartile, medians, third quartile, interquartile range, minimums, and maximums.

In summary statistics of means and medians, one more decimal place beyond the reported data will be displayed, and 2 more decimal places will be displayed for the standard deviation. The minimum and maximum will keep the same decimal places as the reported data.

Statistical tests will be performed at a 2-sided significance level of 0.05 unless otherwise stated. All p-values will be rounded up to 4 decimal places. For example, any p-value strictly greater than 0.0049 and less than or equal to 0.0050 will be displayed as 0.0050. This guarantees that on any printed statistical output, the unrounded p-value will always be less than or equal to the displayed p-value. A displayed p-value of 0.0001 will always be understood to mean ≤ 0.0001 . Likewise, any p-value displayed as 1.0000 will be understood to mean > 0.9999 and ≤ 1 .

All collected data from the eCRFs (including electronic data) and derived analytical data will be included in the listing.

All summaries will be presented by Cohort.

2.1.1 General definitions

As described in the study protocol, fingolimod treatment refers to Fingolimod 0.5 mg/per day.

The last available assessment on or prior to the reference start date is taken as baseline assessment.

For quantitative measurements,

Change from Baseline will be calculated as:

$$\text{Change from baseline} = \text{Test Value at Visit X} - \text{Baseline Value}$$

The date of first administration of fingolimod treatment (Day 1) is defined as the first date when a non-zero dose of fingolimod treatment was administrated. For the sake of simplification, the date of first administration of fingolimod treatment will be also referred to start date of fingolimod treatment.

The date of last administration of fingolimod treatment is derived as the last date on or prior to cut-off date when a non-zero dose of fingolimod treatment was administrated.

The study day describes the day of the event or assessment date, relative to the reference start date (start date of fingolimod treatment or randomization date depending on the type of assessment). The study day will be displayed in data listings. For summaries of vital signs, physical examinations, laboratory data, ECG, etc., assessments will be assigned to a visit based on windowing. Observations from Day 2 through Day 135 will be assigned to the 3-month visit. Days 136 through Day 270 will be assigned to the 6-month visit, and Days 271 and beyond will be assigned to the 12-month visit. If more than one observation occurs within a given window, the one closest to the target day will be used.

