3.1 Study design

This study uses a two-cohort, nonrandomized, open-label, multicenter design.

Cohort 1: In the first cohort approximately 200 patients with RMS, who are newly prescribed commercially available fingolimod 0.5mg/day will participate in the study.

Cohort 2: In the second cohort approximately 200 RMS patients who have been on commercially available fingolimod 0.5mg/day continuously without interruption of treatment for at least ≥ 2 years will participate in the study.

[figure not shown]
Patients from both cohorts will be recruited simultaneously from up to 125 MS centers in the United States. Both cohorts will run concurrently.

The study consists of two periods:

- Screening (up to 4 weeks)
- Treatment period from Baseline (end of screening period considered as Day 1) up to 12 Months

A schema of the study design is presented in [Figure 3-1](#), while a detailed visit and assessment schedule can be found in [Table 6-1](#).

1. An interim analysis will be conducted when 50% of patients in Cohort 2 have completed the Month 6 follow up Visit.
2. A primary analysis will be conducted when all patients complete the Month 6 follow up Visit, which is the primary time point of interest in the study.
3. A final analysis will be completed when all patients have completed the Month 12 follow up Visit of the study.

Figure 3-1 Study design

* Cohort 1: Patients will begin treatment of fingolimod 0.5mg/day for the next 12 Months

** Cohort 2: Patients who have been on fingolimod 0.5mg/day continuously for \geq 2 years will continue treatment of fingolimod 0.5mg/day for the next 12 Months

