5.6.5 Early study termination by the sponsor

The study can be terminated by Novartis at any time for any reason. This may include reasons related to the benefit risk assessment of participating in the study, practical reasons, or for regulatory or medical reasons (including slow enrolment). Should this be necessary, the patient must be seen as soon as possible and treated as a prematurely withdrawn patient. The investigator may be informed of additional procedures to be followed in order to ensure that adequate consideration is given to the protection of the patient's interests. The investigator will be responsible for informing the Institutional Review Board/Independent Ethics Committee (IRBs/IECs) of the early termination of the trial.

6 Visit schedule and assessments

[Table 6-1](#) lists all of the assessments and indices with an "X" when the Visits are performed.

Patients/subjects must be seen for all visits on the designated day, or as close to it as possible. Missed or rescheduled visits should not lead to automatic discontinuation. Patients who prematurely discontinue the study for any reason should be scheduled for a visit as soon as possible, at which time all of the assessments listed for the study discontinuation completion visit (SDC) will be performed.

Table 6-1 **Assessment schedule**

Days/ Months	-Day up to 4 weeks Screening Period	Baseline (Day 1)	Month 3	Month 6	Month 12/ SDC	Unscheduled visit
Visit No	1	2	3	4	5/ 99	
Visit Window (days)			±7	±14	±14/ < 14	
Obtain informed consent	X					
Inclusion/exclusion criteria	X	X				
Demographics	X					
MS medical history / previous therapies	X					
Drug Regimen	X*	X^	X	X	X	X
RMS (Yes/No)	X	X	X	X	X	
Magnetic Resonance Imaging (MRI) review (if available)**	X	X	X	X	X	
Patient Determined Disease Steps (PDDS)***		X	X	X	X	X
Collection of blood samples		X	X	X	X	X
Steroid use for MS	X	X	X	X	X	X
AE /SAE	X	X	X	X	X	X

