2.7 Analysis of the primary objective

2.7.1 Primary endpoint

All analyses will be conducted by cohort for the Safety Set. There are 22 primary endpoints for this study, and Change from Baseline to Month 6 will be calculated as:

Change from baseline to Month 6 = Observed Value at Month 6 (Days 136 to 270) – Baseline Value

1. Change from Baseline to Month 6 in CD4+ naïve T cells (CCR7+CD45RA+)
2. Change from Baseline to Month 6 in CD4+ central memory T cells (CCR7+CD45RACD45RO+)
3. Change from Baseline to Month 6 in CD4+ effector memory T cells (CCR7-CD45RACD45RO+)
4. Change from Baseline to Month 6 in CD4+ Th1 cells (CXCR3+)
5. Change from Baseline to Month 6 in CD4+ Th2 cells (CCR4+)
6. Change from Baseline to Month 6 in CD4+ Th17 cells (CCR6+)
7. Change from Baseline to Month 6 in CD8+ naïve T cells (CCR7+CD45RA+)
8. Change from Baseline to Month 6 in CD8+ central memory T cells (CCR7+CD45RACD45RO+)
9. Change from Baseline to Month 6 in CD8+ effector memory T cells (CCR7-CD45RACD45RO+)
10. Change from Baseline to Month 6 in naïve B Lymphocytes (CD19+CD27-)
11. Change from Baseline to Month 6 in memory B Lymphocytes (CD19+CD27+)
12. Change from Baseline to Month 6 in regulatory B Lymphocytes (CD19+CD24+CD38+)
13. Change from Baseline to Month 6 in monocytes (CD14+)
14. Change from Baseline to Month 6 in neutrophils (CD16+)
15. Change from Baseline to Month 6 in NK cells (CD56+)
16. Change from Baseline to Month 6 in Total CD4+ Absolute Cell Counts
17. Change from Baseline to Month 6 in Total CD4+ Differential Cell Counts
18. Change from Baseline to Month 6 in Total CD8+ Absolute Cell Counts
19. Change from Baseline to Month 6 in Total CD8+ Differential Cell Counts
20. Change from Baseline to Month 6 in Total CD19+ Absolute Cell Counts
21. Change from Baseline to Month 6 in Total CD19+ Differential Cell Counts

Descriptive statistics (sample size, mean, standard deviation, standard error of mean, minimum, first quartile, median, third quartile, interquartile range, and maximum) will be provided. The 95% confidence interval for the mean will be calculated.

Analyses will be performed with respect to the actual value of primary variables by employing an analysis of covariance (ANCOVA) model with gender as a factor and duration of disease at Baseline (either time since first symptom or time since diagnosis) and corresponding baseline as covariates. The unadjusted as well as the adjusted least squares means will be provided together with a p-value.

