2.9 Interim analysis

Two interim analyses of data will be performed prior to the final analysis at Month 12.

1. The first interim analysis is an early assessment to evaluate safety in Cohort 2 patients. This will be conducted when 50% of patients in Cohort 2 have completed the Month 6 follow up. For this analysis, primary variables, demographics, baseline characteristics, adverse events, and serious adverse events will be summarized.
2. The second interim analysis is the primary analysis for this study. This analysis will be conducted when all patients in Cohorts 1 and 2 complete Month 6 (primary time point of interest) of study. All data collected on patients from both Cohorts 1 and 2 will be included in this analysis. These data will be analyzed as mentioned in protocol Sections 9.4, 9.5, and 9.6.

This is an open-label, single arm study, and has no active control. The first interim analysis is a summarization of data from Cohort 2 only and no confirmatory hypothesis will be tested. Thus, the multiplicity adjustment of the level of significance for the primary analysis due to the first interim analysis is not relevant in this study. Results obtained from these interim analyses may be reported and published externally for communication to health care professions, as appropriate.

3 Sample size calculation

Cohort 1: A sample size of 200 patients will be able to detect an effect size of 0.30 with 89% power after adjusting for multiplicity of testing changes in 15 primary variables, at an overall significance level of 0.05.

In addition, for both cohorts the primary interest is to estimate mean change from Baseline at various time points (Months 3, 6, and 12) of the primary and secondary variables. A sample size of 200 patients in each cohort will provide us the precision of estimates within 0.14 of the corresponding standard deviation of the variables of interest.

4 Change to protocol specified analyses

Not applicable.

5 Appendix

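### SAP 2.1.1 sets Day 1 at the first fingolimod dose without limiting it to the study, whereas the protocol sets Day 1 at Baseline; read literally, this empties the Cohort 2 baseline and Month 6 windows

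*SAP*

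**What the plan says.** SAP 2.1.1 describes fingolimod treatment only by its daily dose. It then says that the date of first administration, Day 1, "is defined as the first date when a non-zero dose of fingolimod treatment was administrated". There is no lower bound at study entry and no rule by cohort. The last-dose date in the same section does have a bound, the cut-off date.

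Three rules in SAP 2.1.1 depend on a reference start date:
- Baseline: "The last available assessment on or prior to the reference start date is taken as baseline assessment".
- Study day: counted from the "start date of fingolimod treatment or randomization date depending on the type of assessment".
- Visit windows: Days 2 to 135 are Month 3, Days 136 to 270 are Month 6, and Day 271 onward is Month 12. "If more than one observation occurs within a given window, the one closest to the target day will be used".

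SAP 2.7.1 builds the primary endpoints on the middle window, subtracting the baseline value from the "Observed Value at Month 6 (Days 136 to 270" (days inclusive), by cohort.

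The protocol uses another anchor. Section 3.1 describes the "Treatment period from Baseline (end of screening period considered as Day 1) up to 12 Months", without distinguishing the cohorts, and the Baseline column of Table 6-1 is also labelled Day 1. Under Protocol 3.1, Cohort 2 patients have had at least 2 years of uninterrupted fingolimod 0.5 mg/day. Protocol 6.4.5 records their first-treatment date at Screening, and a treatment date at Baseline for both cohorts. SAP Section 4 declares no change to the protocol-specified analyses.

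**The concern.** For Cohort 1 the first dose is given at Baseline, so the two definitions of Day 1 agree. For Cohort 2 they differ by at least 2 years. The case report form holds both a historical first-treatment date and a Baseline treatment date, and the SAP wording selects the earlier one. The only other anchor that the SAP names, a randomization date, does not exist in a nonrandomized study.

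The Cohort 2 results for change from Baseline to Month 6 are at stake. They matter early, because SAP 2.9 says that "The first interim analysis is a summarization of data from Cohort 2 only" and lists the primary variables among the items to be summarized. The same start date also enters exposure and compliance (SAP 2.6), treatment-emergent status (SAP 2.8.4), imputation of adverse event onset dates (SAP 5.1.2) and the disease-history times (SAP 2.3.4).

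**Working it through.** **The plan's own figures.** SAP Section 3 gives 89% power for Cohort 1 with n = 200, effect size 0.30 and 15 primary variables at overall level 0.05. Assuming a Bonferroni split (the method is not named), the two-sided level is 0.05/15 = 0.00333.
- Normal approximation: Φ(0.30 × √200 − 2.935) = Φ(4.243 − 2.935) = 0.904.
- Noncentral t with 199 degrees of freedom: 0.896.

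Both are within two percentage points of 89%. The precision is 1.96/√200 = 0.139, which matches the stated 0.14. Neither calculation uses Day 1, so neither is affected.

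**Study days for Cohort 2.** Inputs are the SAP 2.1.1 windows, the minimum of 2 prior years taken as 730 days, and nominal visits at 0, 90, 180 and 360 days after Baseline. Blood is drawn at each of these visits (Table 6-1). Study day = prior days + visit offset + 1.

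| Visit | SAP rule, 730 prior days | SAP window | Day 1 = Baseline | SAP window |
|---|---|---|---|---|
| Baseline | 731 | Month 12 | 1 | baseline |
| Month 3 | 821 | Month 12 | 91 | Month 3 |
| Month 6 | 911 | Month 12 | 181 | Month 6 |
| Month 12 | 1091 | Month 12 | 361 | Month 12 |

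Under the literal rule there are 0 baseline values and 0 Month 6 values. Offsets of 91, 183 and 365 days give Days 822, 914 and 1096, with the same outcome. Longer prior treatment only moves the days later. For even the earliest sample to fall by Day 270, prior treatment could be at most 270 − 1 = 269 days, well short of the 730 required.

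Under the protocol anchor, the Table 6-1 visit tolerances give Days 84 to 98 (91 ± 7), 167 to 195 (181 ± 14) and 347 to 375 (361 ± 14). Each range lies inside its intended SAP window.

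Under the literal rule all four samples compete for the Month 12 slot. The SAP states no target day, but any target below (731 + 821)/2 = 776 would keep the Baseline sample as the Month 12 value.

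**Exposure and compliance.** SAP 2.6 takes last dose minus first dose plus 1. A patient dosed through Month 12 has 361 days in the study. From the historical start, 730 + 361 = 1091 days, and 1091/361 = 3.0 times as long. With 5 prior years (1825 days, an assumption) it is 2186 days, or 6.1 times.

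Compliance = (duration − days off treatment)/duration. The missed days below are assumptions. Pre-study missed days are set to 0, because Protocol 6.4.5 asks about missed doses only after Baseline.

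| Missed days in study | Duration 361 | Duration 1091 | Duration 2186 |
|---|---|---|---|
| 18 | 95.0% | 98.4% | 99.2% |
| 36 | 90.0% | 96.7% | 98.4% |
| 72 | 80.1% | 93.4% | 96.7% |

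**Adverse events.** A Cohort 2 event between consent and Baseline would meet the treatment-emergent start condition. A completely missing onset date would be imputed to a day at least 2 years before Baseline.

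**The case against.** The strongest answer is that the documents, read together, give one workable Day 1. SAP 1.1 describes a treatment period from Baseline to 12 Months for both cohorts. The Safety Set in SAP 2.2 requires a dose taken in the study. SAP 2.3.1 counts patients treated and reasons for not being treated, which for Cohort 2 makes sense only for on-study dosing. Protocol 6.4.5 collects a Baseline treatment date in both cohorts. The windows themselves mean nothing for Cohort 2 on any other reading.

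Most of this stands. A reader might infer that the Cohort 2 primary variables cannot be derived at all, or that the first interim analysis is unworkable. The documents do not support that, because both can be produced under the on-study reading. An error that empties every baseline and two of three windows is also unlikely to bias those tables unnoticed.

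The argument does not remove the written conflict. SAP 2.1.1 is the operative definition, it lacks the qualifier that SAP 2.2 has, and the literal reading can be programmed from collected data. Protocol 3.1.2 also says that Cohort 2 continues fingolimod treatment, so the term is not reserved for on-study dosing. A programmer who repaired only the windows could leave exposure, compliance and adverse event dating on the historical date, where the output looks plausible.

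**Conclusion.** The Day 1 definition in SAP 2.1.1 is wrong as written for Cohort 2 and disagrees with the protocol. Applied literally, it leaves about 200 patients with no baseline and no Month 6 value. This needs only the 2-year entry requirement and the SAP's own windows, and it does not depend on how months are converted to days. The 5-year exposure figures and all compliance percentages are illustrations that rest on assumed inputs.

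Severity is minor. The intended anchor can be inferred, and the gross failure would probably be caught at programming. Cohort 2 is a referent cohort with largely descriptive analyses. Cohort 1, power and precision are untouched.

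A reader might also infer that correcting the anchor repairs every use of Day 1. It does not. The SAP 2.3.4 formulas subtract Day 1 from the earlier date, which makes past intervals negative. They also use a diagnosis date for the times from first symptoms and from most recent relapse. Those errors remain whatever Day 1 is.

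**What to change.** In SAP 2.1.1:
- Define the reference start date (Day 1) as the Visit 2/Baseline date for Cohort 2, and as the first fingolimod dose on or after Visit 2 for Cohort 1. Name the visit as well as its number, because Protocol 5.2 labels Baseline Visit 1 while Table 6-1 labels it Visit 2.
- Use this date for baseline, study day, visit windows, treatment-emergent start, adverse event date imputation, and in-study exposure and compliance.
- Delete the reference to a randomization date.

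Separately, correct the SAP 2.3.4 formulas so that each subtracts its own event date (diagnosis, first symptom, most recent relapse) from Day 1.

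Reporting prior fingolimod duration in Cohort 2 as a baseline characteristic is an optional addition.

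The anchor change costs SAP wording and one derivation. It needs no new data, because the Baseline visit date and the historical first-treatment date are already collected.
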